9.2.9 Clinical Laboratory Assessments

All protocol clinical laboratory assessments, as defined in Section 11.1, must be conducted in accordance with the flowchart and the laboratory manual.

9.3 Other Assessments

9.3.1 Demographics and Other Baseline Characteristics

Information on the patient's demographics will be collected during screening in the eCRF.

The following demographic information will be entered:

- Age or date of birth if allowed by local legislation
- Gender
- Ethnic origin if allowed by local legislation
- Race if allowed by local legislation
- Current average alcohol consumption per week, if applicable
- Smoking status, if applicable

9.3.2 Height and Body Weight

Height (without shoes) must be measured at screening and before each cycle and entered in the eCRF (centimeter or inches, one decimal). Body weight (without overcoat and shoes) will be measured at screening and before the first administration of IMP in each cycle and entered in the eCRF (kilogram (kg) or pounds, one decimal). The BSA should be calculated using the Mosteller formula before each treatment cycle for calculation of the IMP doses.

9.3.3 Medical and Surgical History

Information on the patient's medical history, past and all current diseases (including surgical procedures) and general health, will be collected if available during screening and includes, but is not limited to:

- General medical history
- Information on NB diagnosis including tumor characteristics, prior treatment for NB and response to prior treatment, DoR, site(s) of relapse, date of relapse as applicable

A concomitant illness is any illness, other than the disease being investigated, which is present at trial start or found as a result of the screening procedure.

The information collected for medical history and concomitant illnesses includes:

- Diagnosis
- Date of onset
- Date of resolution

Any clinically significant worsening of a concomitant illness that occurs after a patient provided consent must be reported as an AE (Section [10.5](#)).

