10.5 Adverse Event Reporting

10.5.1 Non-Serious Events

Non-serious AEs should be reported from the day of first IMP administration until 42 days after the last IMP administration. Non-serious AEs occurring between signing the ICF and the first IMP administration must be recorded as medical history.

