10.5.2 Serious Adverse Events

Serious AEs should be reported from signing the ICF until 42 days after the last IMP administration.

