10.5.7 Onset Date and Time

Start date for an (S)AE is the date of occurrence of the first symptom. The time should be entered if

- the event starts on an IMP dosing day *or* the day after a naxitamab dosing day
- if the duration of the event is less than 24 hours.

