10.5.9 Severity

The Investigator will use the CTCAE version 5.0 to describe the severity of the AE. If the severity changes over the course of the event, the grade assigned by the Investigator should be the most severe, that occurred during the AE period.

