12.5.1 Adverse events

AE data will be presented descriptively in summary tables and listings. AEs will be regarded as Treatment-Emergent AEs (TEAEs) if they occur after start of first IMP administration.

An infusion/administration related TEAE is an AE that occurs on a day of IMP administration (after start of IMP administration) and is considered related to the IMP treatment.

An infusion related hypersensitivity TEAE is an AE that match a selected list of hypersensitivity terms based on reported preferred terms (including the MedDRA SMQ narrow scopes of anaphylactic reaction, angioedema, hypersensitivity and severe cutaneous reaction), that occurs on a day of naxitamab infusion (after the infusion start) or the day after a naxitamab infusion irrespectively of relatedness to naxitamab.

AEs with onset during the pre- and post-treatment period will be listed. AEs with onset during the on-treatment period will be summarized as follows: summaries of AEs will be presented for all TEAEs, IMP-related TEAEs, CTCAE Grade 3 or higher TEAEs, IMP-related CTCAE Grade 3 or higher TEAEs, infusion/administration-related TEAEs, infusion-related hypersensitivity TEAEs, SAEs, IMP-related SAEs, CTCAE Grade 3 or higher SAEs, IMP-related CTCAE Grade 3 or higher SAEs, TEAEs leading to treatment discontinuation, AEs leading to death.

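### Sections 9.3.3 and 10.5.1 conflict on non-serious worsening of a concomitant illness before first IMP, and Section 12.5.1 has no clause for events that start before IMP and worsen after it, so the same clinical course may or may not be counted as treatment-emergent

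*Combined protocol and SAP*

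**What the plan says.** **Before first IMP.** Section 9.3.3 makes worsening after consent reportable whatever its seriousness: "Any clinically significant worsening of a concomitant illness that occurs after a patient provided consent must be reported as an AE". It refers the reader to Section 10.5. There, Section 10.5.1 opens the non-serious window later: "Non-serious AEs should be reported from the day of first IMP administration until 42 days after the last IMP administration". It adds: "Non-serious AEs occurring between signing the ICF and the first IMP administration must be recorded as medical history". Section 10.5.2 sets a different start for serious events: "Serious AEs should be reported from signing the ICF until 42 days after the last IMP administration".

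**How one event is recorded.** Section 10.5.7: "Start date for an (S)AE is the date of occurrence of the first symptom". Section 10.5.9 says that if severity changes during an event, "the grade assigned by the Investigator should be the most severe, that occurred during the AE period". Under Section 10.8, a change in intensity of an ongoing SAE is reported as follow-up on that event.

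**When worsening is an event of its own.** Section 10.1 counts clinically significant worsening of a concomitant illness as an AE. It also makes a pre-existing condition reportable if it worsens during the AE reporting period.

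**What is tabulated.** Section 12.5.1: "AEs will be regarded as Treatment-Emergent AEs (TEAEs) if they occur after start of first IMP administration". The summaries, including those of Grade 3 or higher TEAEs and of SAEs, are restricted to on-treatment onset. For the rest, "AEs with onset during the pre- and post-treatment period will be listed".

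**The concern.** For a non-serious worsening of a concomitant illness between consent and first IMP, the two rules cannot both be followed. The cross-reference from 9.3.3 to 10.5 does not settle it, because 10.5.1 is the other half of the conflict. Other parts of the protocol make it plausible that sites will open AE records before IMP. The flow chart collects AEs during screening, 10.5.5 asks for every event meeting the AE definition, and 10.5.12 provides an action code for AEs before first treatment. These provisions also serve SAEs, but none is limited to them.

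The choice of route can decide whether later worsening on treatment reaches the safety tables. AE incidence by CTCAE grade is secondary endpoint 13 in Section 6.2. The trial has one arm, so there is no control group in which inconsistent recording could cancel out. Where a case is lost, the loss lowers the on-treatment toxicity count.

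**Working it through.** There is no stated figure to reproduce. The check follows one clinical course through the sections.

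**Example.** A patient has a neuropathy left by earlier chemotherapy. It worsens to Grade 2 after consent and before first IMP, is not serious, is still present at first IMP, and reaches Grade 3 on treatment.

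1. *Site follows 10.5.1.* The Grade 2 worsening is medical history. The condition was present before the non-serious reporting window opened, so under 10.1 the later worsening is a new AE with on-treatment onset. It is counted as a TEAE and as a Grade 3 or higher TEAE.
2. *Site follows 9.3.3 and keeps one record.* The AE starts before IMP (10.5.7) and ends up carrying Grade 3 (10.5.9). Its onset lies in the pre-treatment period of Section 12.5, so it is listed and appears in no TEAE summary. If it also becomes serious on treatment, it is missing from the SAE summary as well.
3. *Site follows 9.3.3 but opens a new AE under 10.1 at the on-treatment worsening, or the event resolves before IMP and then recurs.* The new record has on-treatment onset and is counted.

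The course is the same in routes 1 and 2, and the table entry differs.

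**Serious events.** Sections 9.3.3 and 10.5.2 agree that a serious worsening after consent is reported, so the first conflict disappears. The gap in 12.5.1 remains and is clearest here. The SAE reporting period starts at consent, so an SAE arising after consent does not fit the pre-existing-condition rule of 10.1. Section 10.8 treats its later change in intensity as follow-up on the same event. A pre-IMP SAE that worsens on treatment is therefore most naturally one record with a pre-treatment onset, which is listed and not tabulated.

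**Size.** Section 7.1 plans 52 enrolled patients, all with at least one dose of IMP, and all of them enter the safety set of Section 12.3. If k patients are lost from a given table row and are not counted in it through another event, the rate falls by k/52:

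- k = 0: 0 points
- k = 1: 1/52 = 1.9 percentage points

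The documents give nothing from which to estimate k. The window is short: screening starts at about Day -24 and IMP on Day 1.

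**The case against.** The strongest reply is that Section 10.1 already provides the remedy. Worsening of a concomitant illness is itself an AE, and neither 10.5.7 nor 10.5.9 forbids a second record for a second worsening. This stands in part. A reader might infer that an event opened before IMP can never reach the TEAE tables, and the documents do not support that, because route 3 is open to any site that reads 10.1 this way. Nor does the loss follow from the TEAE definition alone. That sentence speaks of events that occur after first IMP; onset governs the sentences on summaries and listings, and 10.5.7 and 10.5.9 must also be read as keeping one record. What remains is that nothing tells the site which reading to use, and for SAEs the text leans towards one record.

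The conflict is also narrow. Section 9.3.3 concerns only a concomitant illness, meaning one other than neuroblastoma that is present at trial start or found at screening. Tumour pain is excluded. New non-serious events in the window, such as pain after a marrow biopsy or an effect of gabapentin, fall under 10.5.1 alone.

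A reader might put the understatement at about 2 to 8 points by supposing 1 to 4 affected patients (1/52 = 1.9%, 4/52 = 7.7%). Those counts would be pure assumption, and zero is possible. A fall of 7.7 points in one event term would need all four patients to share that term. In the any-Grade-3-or-higher row, most patients would probably be counted anyway: Section 4.3.2 reports such rates of up to 92% in the earlier naxitamab trials, which here would be 0.92 × 52 = about 48 patients.

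Finally, Sections 12.5 and 12.13 defer detail to a separate SAP, and 10.7 points to eCRF completion instructions. Neither text is in the document reviewed, and either might contain a worsening rule. An SAP rule alone could not fully repair the data, however. Section 9.3.3 collects diagnosis and dates for concomitant illness but no grade, and 10.5.9 keeps one grade per event. Serious events are not hidden in any case, since they are reported promptly and listed; what is affected is their place in the tables.

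**Conclusion.** The contradiction between 9.3.3 and 10.5.1 is confirmed for non-serious, clinically significant worsening of a concomitant illness between consent and first IMP. The missing worsening clause in 12.5.1 is also confirmed. The consequence is conditional: an event opened before IMP, still ongoing and kept as one record is left out of the TEAE, Grade 3 or higher and SAE summaries, while the same course recorded as medical history or as a new AE is counted.

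The size is at most 1.9 percentage points per affected patient in any one table row, for an unknown and possibly zero number of patients. This rests on the planned 52 patients and on the absence of a worsening rule in the SAP or the eCRF instructions. The primary endpoint and its power are not touched. The point is worth correcting because it makes a secondary safety endpoint depend on which section a site happens to follow.

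**What to change.** 1. Make 9.3.3 consistent with 10.5.1: non-serious worsening before first IMP is medical history, recorded with its CTCAE grade at first IMP.
2. State in Section 10.5 that any pre-IMP condition or SAE that increases in grade or becomes serious after first IMP is entered as a new AE dated at the worsening, as an explicit exception to the start-date rule in 10.5.7. A new record is needed because a single worst grade does not show when it was reached.
3. In 12.5.1, define a TEAE as an AE that starts, or worsens in grade or seriousness, after start of first IMP administration, and apply the same rule to the summary tables. Confirm that the SAP uses the same definition.

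The cost is some protocol and SAP wording, a baseline-grade field in the eCRF for conditions ongoing at first IMP, and some additional AE records. No dose, visit or clinical rule changes.

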9.3.4 Performance Test

A performance test will be performed at screening, prior to each cycle and EOT. The scales to be used are Lansky for children < 16 years of age and Karnovsky for adolescents and adults \geq 16 years of age. Please refer to [Appendix 10](#). The same scale must be used during the trial, also if the patient turns 16 years during the trial.

9.3.5 Unscheduled Visits

If any assessments need re-evaluation, an additional response assessment is needed, or follow up on an (S)AE is required, the patient can be called for an unscheduled visit at the discretion of the Investigator. Data obtained during unscheduled visits pertaining to the clinical trial will be collected as unscheduled visits in the eCRF.

10 ADVERSE EVENTS

10.1 Definition of Adverse Events

An AE is any untoward medical occurrence in a patient administered a pharmaceutical product which does not necessarily have a causal relationship with the treatment.

An AE can, therefore, be any unfavorable and unintended sign (including an abnormal laboratory finding), symptom, or disease temporally associated with the use of a product, whether or not considered related to the product.

An AE includes:

- A clinically significant worsening of a concomitant illness.
- A laboratory abnormality which is clinically significant, i.e., an abnormality that suggests a disease and/or organ toxicity and is of a severity that requires active management. Active management includes interventional treatment or further investigations, for example change of medicine dose or more frequent follow-up due to the abnormality.

Pre-existing condition, (i.e., a disorder present before the AE reporting period started and noted on the medical history/physical examination form) should not be reported as an AE unless the condition worsens, or episodes increase in frequency during the AE reporting period.

Diagnostic and therapeutic non-invasive and invasive procedures, such as surgery, should not be reported as AEs. A medical condition for which an unscheduled procedure was performed should, however, be reported if it meets the definition of an AE. For example, an acute appendicitis should be reported as the AE and not the appendectomy.

10.2 Definition of Serious Adverse Events

Each AE is to be classified by the Investigator as either serious or non-serious. This classification of the seriousness of the AE determines the reporting procedures to be followed. An AE that meets one or more of the following criteria/outcomes is classified as serious:

- Is fatal or life-threatening¹
- Requires inpatient hospitalization or prolongation of existing hospitalization²
- Results in persistent or significant disability/incapacity
- Is a congenital anomaly/birth defect
- Medically important event³

¹: The term "life-threatening" in the definition of "serious" refers to an event in which the patient, in view of either the Investigator or Sponsor, was at risk of death at the time of the event; it does not refer to an event, that hypothetically might have caused death if it was more severe. Death alone is not considered an AE; it is an outcome of an AE.

Reports of death should be accompanied by the corresponding AE term for the event that led to death. However, sudden death or death due to unexplainable cause should be reported as an SAE, while follow-up is pursued to determine the cause.

²: Hospitalization is defined as admission to a hospital/inpatient (irrespective of the duration of physical stay) or is not admitted to a hospital/not an inpatient but stays at the hospital for treatment or observation for more than 24 hours. Events leading to hospitalizations for the following reasons should not be reported as SAEs:

- Trial-related purposes, not associated with any deterioration in condition
- Social reasons in the absence of any deterioration in the patient's general condition
- Elective surgery or other scheduled hospitalization periods that were planned before the patient was included in this trial.

³: Medical and scientific judgment must be exercised in deciding whether an AE is believed to be "medically important". Medically important events may not be immediately life-threatening or result in death or hospitalization but may jeopardize the patient or may require intervention to prevent one of the other outcomes listed in the definition above.

10.3 Definition of Non-Serious Adverse Events

A non-serious AE is any AE which does not fulfil the definition of an SAE.

10.4 Definition of Predefined Adverse Events of Special Interest

The following AEs (serious and non-serious) are selected as AEs of Special Interest (AESIs):

- Hypertension:
 - Requiring antihypertensive therapy or
 - Which persists at the 90th percentile or higher for age, height and sex and requires additional monitoring after naxitamab infusion according to Section 8.4.5.3
- Hypotension CTCAE Grade 3
- AEs leading to incomplete dosing of naxitamab during a cycle (i.e., the total planned dose of naxitamab was not given in a cycle)

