8.1.2.3 Naxitamab

On days when co-administered with GM-CSF, naxitamab infusion is started ≥ 60 min after GM-CSF.

On days when co-administered with IT (i.e., Days 2 and 4), it is recommended to start naxitamab infusion at least 1 hour after irinotecan administration to allow for preparations and administration of pre-medications.

Naxitamab should be infused IV at 2.25 mg/kg/day on Days 2, 4, 8 and 10 for a total dose of 9 mg/kg per cycle (Please refer to Appendix 2 for details on naxitamab treatment if the patient has discontinued IT treatment due to toxicity). Administration of naxitamab should be adjusted according to Section 8.4.5, if selected naxitamab adverse reactions are observed. If any events occur fulfilling a general discontinuation criterion the patient must be withdrawn from all treatments immediately and enter long-term FU, see Section 7.12.

At Cycle 1 Day 2 (C1D2):

Naxitamab should be infused over approximately 60 min.

All subsequent naxitamab infusions:

Naxitamab should be infused over approximately 30 min.

Special circumstances

The infusion may be given over approximately 60 min. at Day 2 of any cycle at the investigator's discretion if:

- The patient during C1D2 experienced naxitamab related hypotension:
 - Grade 4 **or**
 - Grade 3 not adequately responding to intervention
- At the investigator's discretion due to severe infusion related adverse drug reactions not adequately responding to interventions

The 60/30 min infusion time is a minimum infusion time. If infusion pause or infusion rate reduction is required due to infusion related AE (see Section [8.4.5](#)) the infusion time will become longer.

Naxitamab treatment in an out-patient setting is defined as a naxitamab infusion performed in the ambulatory setting.

In-patient treatment (i.e. requiring hospitalization) includes both short term admissions and admissions requiring overnight stay.

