8.4.5.2 Management of hypotension

Hypotension Grade 2

- Administer 0.9% saline bolus 10-20 mL/kg IV over 5-15 min

Hypotension Grade 3 without other signs or symptoms

- Decrease naxitamab infusion rate to approximately 50%
- Administer IV 0.9% saline bolus 10-20 mL/kg over 5-15 min. Monitor blood pressure (BP) closely (at least after completion of the bolus and again 15 min later)
 - If the patient remains hypotensive, repeat bolus as described above (maximum a total of 60 mL/kg) and consider additional treatments as described below
 - If the patient stabilizes, consider increasing to the infusion rate prior to the event

Hypotension Grade 3 with other signs or symptoms such as bradycardia, hypoxia, not adequately responding to treatment or Grade 4 hypotension

- Pause naxitamab infusion
- Initiate aggressive fluid resuscitation according to local standard of care (e.g., American College of Critical Care Medicine (ACCC)⁴¹)
- Monitor vital signs closely
- If the patient remains hypotensive, repeat IV 0.9% saline bolus as described above
 - If resolution to CTCAE \leq Grade 2: resume naxitamab infusion at approximately 50% of the previous infusion rate. If the patient has stabilized and the naxitamab infusion is well tolerated increase to the infusion rate prior to the event at the discretion of the investigator

- If the patient remains hypotensive, consider additional treatments as described below
- If the patient is NOT warm and well-perfused **or** do not respond satisfactorily to IV 0.9% saline bolus treatments **or** does respond to IV 0.9% saline bolus but only temporarily, the following should be considered:
 - Give naloxone if the patient is difficult to arouse
 - If naloxone has no effect or based on clinical judgement, consider administration of an inotrope/pressor according to local SoC (e.g., epinephrine IV/intramuscular (IM))
 - If desired effect is achieved and the hypotension is CTCAE \leq Grade 2, consider resuming naxitamab infusion at 50% of the previous infusion rate. If hypotension CTCAE Grade 3 occurs again consider halting naxitamab infusion
 - If the patient continues to be hypotensive and difficult to arouse, stop the current naxitamab infusion permanently and initiate appropriate treatment and observations at the discretion of the investigator (e.g., hospitalization in the intensive care unit)

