10.8 Follow-up on Adverse Events

SAE/AESIs:

- New follow-up information available at site must be reported within 24 hours of knowledge.
- Follow-up information requested from Sponsor must be replied to within three working days. The eCRF AE form should be updated in accordance to agreed data entry timelines (see Section 15.2.2).
- If an ongoing SAE/AESI changes in intensity, relationship to IMP or as new information becomes available for the event, the paper Clinical AE Report Form should be completed and sent to the designated drug safety provider within 24 hours of the change in assessment (see Section 10.6).
- Grade 3 or higher non-serious AEs that are considered treatment related and all SAEs (including AESIs) should be followed on a regular basis, according to the Investigator's clinical judgment, until the event has been resolved or until the Investigator can assess it as chronic or stable. This includes follow-up after EOT

Non-SAEs

Non-serious AEs should be followed until they are either resolved, returned to baseline, or until 42 days after last dose of IMPs, whichever comes first

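### The hypotension item in the AESI list is written as Grade 3 only, so hypotension with worst grade 4 or 5 does not meet it; the effect is confined to AESI classification

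*Combined protocol and SAP*

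**What the plan says.** Section 10.4 opens its list with "The following AEs (serious and non-serious) are selected as AEs of Special Interest (AESIs" and then gives three items. These are hypertension that needs treatment or persists above a stated percentile, "Hypotension CTCAE Grade 3", and "AEs leading to incomplete dosing of naxitamab during a cycle". The hypotension item carries no qualifier for higher grades.

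Section 10.5.9 says that if severity changes during an event, "the grade assigned by the Investigator should be the most severe, that occurred during the AE period".

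Grade 4 hypotension is provided for in two places. Section 8.4.5.2 has a management block whose heading includes "not adequately responding to treatment or Grade 4 hypotension". Section 8.1.2.3 allows a longer infusion time if "The patient during C1D2 experienced naxitamab related hypotension", with Grade 4 as the first case listed. Appendix 2 repeats this provision for patients on naxitamab and GM-CSF alone.

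**The concern.** A severity threshold for an event of special interest is normally a floor. Here it is written as a single grade. Combined with worst-grade recording, the item takes hypotension that peaks at Grade 3 and leaves out hypotension that goes further. Anyone who later selects hypotension AESIs from the database by this definition would get a set without its most severe members, and the count could be lower because events were worse.

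The risk is a relevant one. Section 4.3.2 names hypotension among the Grade 3 or higher events reported in at least 10% of patients in one or both earlier naxitamab trials.

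**Working it through.** This is a question of wording; there is no plan figure to reproduce and no calculation to run. The check sets the relevant sections side by side.

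1. **What the item covers.** Section 10.4 gives Grade 3 alone, and no other section extends it. Read literally, the item contains events with worst grade exactly 3. If n3, n4 and n5 are the numbers of hypotension events by worst grade, the item counts n3, while an or-higher item counts n3 + n4 + n5. The difference is n4 + n5. The readable text gives no value or range for either term.

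2. **Whether the limit looks deliberate.** The documents give no reason for it. The AESI list expressly includes serious events, so Grades 4 and 5 are not left out because they are SAEs. Where the protocol wants a floor it writes one: "Grade 3 or higher non-serious AEs that are considered treatment related" in Section 10.8, "CTCAE Grade 3 or higher TEAEs" in Section 12.5.1, a greater-than-or-equal sign for the GM-CSF reactions in Sections 7.12 and 8.4.6, and an or-higher percentile for hypertension in the same AESI list.

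3. **Whether the third AESI item closes the gap.** It does so only in part. It applies when the planned naxitamab dose for the cycle was not all given. Section 8.4.5.2 calls for a pause at Grade 4 and then allows the infusion to resume once hypotension has improved to Grade 2 or lower. Section 8.1.2.3 describes later infusions in patients who had Grade 4 hypotension on Cycle 1 Day 2, and Section 7.12 does not name hypotension as a discontinuation criterion. A Grade 4 event with the full cycle dose delivered is therefore possible under the protocol, and it would meet none of the three items. An event that the third item does catch is an AESI because of the dosing, not as hypotension.

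4. **What happens to reporting.** Section 10.2 makes fatal or life-threatening events SAEs. Sections 10.5.5, 10.6 and 10.7 put SAEs and AESIs on the same forms and the same 24-hour timeline, and Section 10.8 follows both in the same way. For any event that meets an SAE criterion, nothing is lost or delayed.

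5. **What happens to the planned analyses.** Section 12.5.1 lists summaries of Grade 3 or higher events, SAEs, Grade 3 or higher SAEs and AEs leading to death, among others. On-treatment Grade 4 and 5 hypotension enters the summaries that apply to it at its recorded grade. The section lists no AESI summary, so no analysis stated in the documents changes.

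**The case against.** The strongest reply is that nothing visible is harmed. Expedited reporting runs through the SAE route, the planned tables show these events at their true grade, and no AESI table is planned. All of this stands, and it limits the point to classification.

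A reader might infer two stronger things that the documents do not support.

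- **That the monitoring committee or the study report will see severe hypotension understated.** Section 10.11 has the committee review accumulating data about every three months and ad hoc, and does not restrict it to AESIs. Its procedures are in a charter, and further safety analyses are deferred to a separate SAP (Sections 12.5 and 12.13); neither is in the supplied text. A biased AESI count is possible if one is produced from this definition, but none is shown to be planned.
- **That a Grade 3 event which worsens loses its AESI status.** An event reported while at Grade 3 is already an AESI. Section 10.8 expects an ongoing AESI to change in intensity and requires an updated form within 24 hours. No section declassifies it. The documents do not say how its final classification is set once the recorded grade is 4. The clear gap is for events that are already Grade 4 or 5 when first reported.

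It would also be too broad to say that all Grade 4 or 5 hypotension is outside the AESI list, since the third item takes some of it.

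What the reply does not do is explain the wording. A definition meant to single out severe hypotension should include the most severe cases without relying on other routes to catch them.

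**Conclusion.** The point holds for the hypotension item as written: worst grade 4 or 5 does not meet it, and nothing in the documents shows that this is intended. It is a minor definitional fault. It touches neither the primary analysis nor any summary listed in Section 12.5.1, and it does not affect expedited reporting of events that meet the SAE definition. Its reach is AESI classification and any AESI-based listing or count. Its numerical size is unknown.

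The conclusion rests on a literal reading of Section 10.4 and on Section 10.5.9 being applied as written. The protocol does not reproduce the CTCAE grade definitions, so the statement about reporting is made for events that meet an SAE criterion, not for every Grade 4 event as such.

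**What to change.** Change the Section 10.4 bullet to: Hypotension CTCAE Grade 3 or higher. This also settles the classification of an event that worsens from Grade 3, because its worst grade then still meets the item.

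The cost is two words, plus the matching edit in any reporting instructions that repeat the definition. Protocol changes go through the submissions described in Section 14.3, so the edit can wait for the next amendment. Extra reporting would be negligible: events that meet the SAE definition already use the same forms and timeline, and only a Grade 4 event that met no SAE criterion and no other AESI item would be new to that route. No dose, treatment rule or planned analysis changes.
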